7 STUDY ENDPOINTS

- To support a dose of atorvastatin injection that adequately replaces oral atorvastatin, the following primary endpoint will be evaluated for each of the three, labelled oral doses of atorvastatin (10, 20, and 40 mg daily); endpoints are assessed using the subjects' levels of (LDL-C) and high-density lipoprotein cholesterol (HDL-C):
 - Eleven or more subjects in a dosing cohort of thirteen with a Day 15 LDL-C not more than 125% of their baseline LDL-C.

Secondary endpoints that contribute to the same objective are as follows:

- Eleven or more subjects in a dosing cohort of thirteen with a Day 15 HDL-C not less than 75% of their baseline HDL-C.

- The mean change in LDL-C at Day 15 for each treatment cohort (N=13)
- To compare the pharmacokinetic profile of atorvastatin administered by the intravenous route to that of oral administration, the following parameters of atorvastatin, 2-hydroxy atorvastatin and 4-hydroxy atorvastatin will be calculated for each of the three final IV treatment cohorts (See [Study Design](#) for description of the three cohorts):
 - Maximum serum concentration (C_{max})
 - Area under the curve to infinity (AUC_{inf})
 - Area under the curve to 24 hours (AUC_{0-24})
 - Elimination half-life ($T_{1/2}$)
 - Volume of distribution at steady state (VD_{ss})
 - elimination rate constant (K_{el})
 - Clearance (Cl)
- To explore the pharmacokinetic profile of atorvastatin administered by the subcutaneous route, the following parameters of atorvastatin, 2-hydroxy atorvastatin and 4-hydroxy atorvastatin will be calculated for each of the three final treatment cohorts (See [Study Design](#) for description of the three cohorts):
 - C_{max}
 - AUC_{inf}
 - AUC_{0-24}
 - $T_{1/2}$
 - VD_{ss}
 - K_{el}
 - Cl/F
 - Cl
- To assess the safety of the study drug, the following will be evaluated:
 - Adverse events
 - Mean change (baseline to Day 15) for creatine phosphokinase (CPK), alanine aminotransferase (ALT) and aspartate aminotransferase (AST) in each dosing cohort.

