- To compare the PK profile of atorvastatin administered by the IV route to that of oral administration, the following parameters of atorvastatin, 2-hydroxy atorvastatin and 4-hydroxy atorvastatin will be calculated for each of the four final multiple dosing injectables (IV and SC) treatment cohorts:

- Maximum serum concentration (C_{max})
 - Area under the curve to infinity (AUC_{inf})
 - Area under the curve to 24 hours (AUC_{0-24})
 - Elimination half-life ($T_{1/2}$)
 - Volume of distribution at steady state (Vd_{ss})
 - Elimination rate constant (K_{el})
 - Clearance (CL)

- To explore the PK profile of a single dose of atorvastatin administered by the SC route, the following parameters of atorvastatin, 2-hydroxy atorvastatin and 4-hydroxy atorvastatin will be calculated for each of the three final treatment cohorts:

- C_{max}
 - AUC_{inf}
 - AUC_{0-24}
 - $T_{1/2}$
 - Vd_{ss}

- K_{el}
- Apparent clearance (CL/F)
- To assess the safety of the study drug, the following will be evaluated:
 - Adverse events
 - Mean change (baseline to Day 15) for creatine phosphokinase (CPK), alanine aminotransferase (ALT) and aspartate aminotransferase (AST) in each dosing cohort.

4 Study Design and Methods

This is a Phase II, open-label, single-center dose-ranging study.

Three treatment cohorts of 13 subjects each are planned for intravenous route of administration. The different cohorts are composed of subjects taking three of the four commercially-prescribed levels of daily oral dosing: 10, 20, and 40 mg. The 4th Cohort for 80 mg oral dosing did not proceed with enrollment (per Amendment 3). Instead a 4th Cohort of 10 subjects (Amendment 03 of the protocol (Sections 9.3.6.2.3 and 12.2)) following the daily oral dosing of 20 mg will receive 15 days of subcutaneous treatment with atorvastatin. Subjects are treated with daily doses of injectable atorvastatin intended to be non-inferior to the efficacy of their stable oral dose at baseline.

Enrollment of subjects into any one of the cohorts that does not prove to meet the primary endpoint is terminated as soon as this determination is made, and a new cohort intended for 13 subjects is opened at an adjusted dose with intentions to meet the primary endpoint (See Table 1).

Table 1: Treatment Assignment – Main Study

Cohort	Lead-in Daily Dose of Oral Atorvastatin	Initial Targeted, Daily IV or SC Atorvastatin Dose	Maximum Daily IV or SC Atorvastatin Dose, after Escalations	Subjects
1	10 mg	2 mg IV	5 mg IV	13

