5.7.2 Pharmacokinetic Parameters

Pharmacokinetic parameters will be derived for atorvastatin and its metabolites for subjects in the PK population.

Pharmacokinetic parameters are defined in Table 4.

Table 4: Pharmacokinetic Parameters

Parameter	Description
C_{\max}	Maximum plasma concentration
AUC_{0-24}	Area under the plasma concentration-time curve from time zero to 24 hours
AUC_{∞}	Area under the plasma concentration-time curve from time zero to infinity
T_{\max}	Time to reach maximum plasma concentration
$T_{1/2}$	Elimination half-life
K_{el}	Elimination rate constant
$Cl(/F)$	(Apparent) clearance of drug from plasma for extravascular dosing
VD_{ss}	Volume of distribution at steady state for intravenous dosing
V_z/F	Apparent volume of distribution for extravascular dosing

Pharmacokinetic parameters will be calculated using noncompartmental methods and actual blood sampling times. In case of missing actual time, planned (or nominal) time will be used.

Concentration listed as below the limit of quantitation will be set to zero for the calculations. If a sample is missing or the value is not reportable and is between two measurable concentrations, the value at that time point will be left blank for the analysis and reported as either Not Reportable (NR) or No Sample (NS).

The PK timepoint at 24-hour post oral dosing is the pre-dose concentration due to reaching steady state. The first timepoint immediately following IV bolus dosing is set as 0.0055 hour (assume 20 seconds bolus dosing). The 24-hour post-dose concentration is set as pre-dose concentration before IV and multiple-dose SC dosing. For the single dose SC (sub-study) the pre-dose concentration is the 24-hour post-oral dose concentration.

No value of K_{el} , AUC_{∞} or $t_{1/2}$ will be reported for cases that do not exhibit a terminal log-linear phase in the concentration versus time profile. If the adjusted R-squared value ($Rsq_{adjusted}$) is < 0.8 , the analyst may evaluate if other time points are more appropriate and use those for the calculation of K_{el} , or no value of K_{el} , AUC_{∞} or $t_{1/2}$ will be reported.

For determination of AUC_{∞} , if calculated AUC from last to infinity is greater than 20% of the calculated AUC from 0 to infinity, then AUC_{∞} will not be reported.

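### Clearance and VDss are listed for the two metabolites, where values based on the parent dose are only apparent quantities; for SC parent drug the endpoint lists also conflict with SAP Table 4

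*SAP*

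**What the plan says.** Three places set out which PK parameters are derived, and for which analytes.

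- **SAP section 3, multi-dose list.** "the following parameters of atorvastatin, 2-hydroxy atorvastatin and 4-hydroxy atorvastatin will be calculated for each of the four final multiple dosing injectables" cohorts. These comprise three intravenous (IV) cohorts and Cohort 4, which is SC only. The list includes VDss and plain CL, with no limit by route or analyte.
- **SAP section 3, single-dose SC list.** "the following parameters of atorvastatin, 2-hydroxy atorvastatin and 4-hydroxy atorvastatin will be calculated for each of the three final treatment cohorts". This list also includes VDss, but gives clearance as CL/F.
- **Protocol section 7, SC list.** "To explore the pharmacokinetic profile of atorvastatin administered by the subcutaneous route, the following parameters of atorvastatin, 2-hydroxy atorvastatin and 4-hydroxy atorvastatin" include VDss, Cl/F and, separately, plain Cl. The protocol's IV list has VDss and Cl for the same three analytes.

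The analysis section of the SAP is more careful about route. Table 4 in 5.7.2 describes VDss as "Volume of distribution at steady state for intravenous dosing", gives Vz/F as the volume term for extravascular dosing, and writes clearance as Cl(/F). It is not more careful about analyte: "Pharmacokinetic parameters will be derived for atorvastatin and its metabolites for subjects in the PK population", and no row of Table 4 is restricted to the parent drug. Vz/F appears in none of the endpoint lists.

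**The concern.** Clearance and volume need a known amount of the measured substance entering the circulation. For atorvastatin given IV that amount is the dose. For the two hydroxy-metabolites it is unknown: they are formed in the body, and the documents give neither a fraction formed nor a rule confining these parameters to the parent. A non-compartmental calculation using the parent dose gives a figure that looks like a clearance but mixes elimination with formation.

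This matters most for the comparison that the PK objective is about. Protocol section 5.4 says that the systemic parent-to-metabolite ratios change when atorvastatin is given IV instead of orally. If the routes differ in how much metabolite is formed, a parent-dose-based metabolite clearance will differ between them for that reason alone, and a reader of the tables could take it for a difference in elimination.

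For SC parent drug the issue is smaller. The endpoint lists and Table 4 name different parameters, so an analyst cannot satisfy both.

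**Working it through.** The documents state no clearance, volume, SC bioavailability (F) or fraction formed (fm), so there is no figure of the plan to reproduce. The check is algebraic. All values of F, fm and the rate constants below are assumptions used to show the range.

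**Inputs from the documents.** Non-compartmental method (SAP 5.7.2); parent drug is the only substance dosed; parameter lists as set out above; planned bioavailability comparisons are oral against IV and oral against SC only (SAP 5.1 and 5.7.3).

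**1. Metabolite clearance after an IV parent dose.** With dose and AUC in consistent molar units, AUC_m = fm × Dose / CL_m. Hence

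Dose / AUC_m = CL_m / fm.

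The overstatement is 1/fm:

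| Assumed fm | Overstatement of CL_m |
|---|---|
| 0.75 | 1/0.75 = 1.33 times |
| 0.5 | 1/0.5 = 2 times |
| 0.25 | 1/0.25 = 4 times |
| 0.1 | 1/0.1 = 10 times |

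**2. Metabolite volume.** The steady-state volume formula applied to the metabolite profile gives

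Dose × AUMC_m / AUC_m² = (V_m / fm) × (1 + MRT_parent / MRT_m).

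It carries the 1/fm factor and a second factor for the time that the drug spends as parent. In a one-compartment example with fm = 0.25 and elimination rates of 0.2/h for parent and 0.4/h for metabolite, MRT_parent / MRT_m = 0.4/0.2 = 2, so the overstatement is (1 + 2)/0.25 = 12 times. Numerical integration of the profile also gave 12.0.

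**3. Comparison between routes.** Hold CL_m fixed and let the fraction of the dose that reaches the circulation as metabolite be 0.25 by one route and 0.5 by the other (assumed). Dose-based clearance is then 4 × CL_m by the first route and 2 × CL_m by the second. That is an apparent two-fold difference with no difference in elimination.

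**4. SC parent drug, lists against Table 4.**

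| Source | Volume for SC | Clearance for SC |
|---|---|---|
| SAP 3, multi-dose (includes SC Cohort 4) | VDss | CL |
| SAP 3, single-dose SC | VDss | CL/F |
| Protocol 7, SC list | VDss | Cl/F and Cl |
| SAP Table 4 | Vz/F (VDss is for IV) | Cl(/F), apparent for extravascular dosing |

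If the endpoint lists were followed literally, Dose/AUC = CL/F would be labelled CL, an overstatement of 1/F: 1/0.8 = 1.25 times at F = 0.8 and 1/0.5 = 2 times at F = 0.5. A VDss computed from an SC profile would be overstated by (1 + MAT/MRT_IV)/F, where MAT is the mean absorption time. At F = 1 and a ratio of 0.1 this is 1.1 times; at F = 0.5 and a ratio of 1 it is 2/0.5 = 4 times. A numerical check with F = 0.5, absorption rate 1.0/h and elimination rate 0.2/h gave 2.0 times for clearance and 2.4 times for volume, which agrees with (1 + 0.2)/0.5.

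**The case against.** The strongest reply is that the SAP already handles route. Table 4 is where the parameters are defined, and both it and the SAP abbreviation list keep VDss for IV dosing and provide apparent terms for extravascular dosing. An analyst working from Table 4 would report CL/F and Vz/F for SC parent drug. That stands. A reader might infer from the endpoint lists that wrong SC values are bound to be reported, but the documents do not support this; they show two sections that disagree. Nor does the complaint about unqualified clearance reach the SAP's single-dose SC list, which already has CL/F.

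A reader might also infer that parent clearance and VDss cannot be obtained in anyone who receives SC drug. That is too strong as well. Sub-study participants in Cohorts 1 to 3 have a Day 15 IV profile, and their SC dose is the same quantity, so parent CL and VDss come from the IV data. An SC-to-IV ratio could in principle be estimated, although none is planned and the SC day follows a period of oral dosing. Only Cohort 4 has no IV profile in the same subjects.

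The size is also open to challenge: no value of fm or F is in the documents, so the multiples depend on what is assumed. This is correct, and they are only illustrations. The form of the error, 1/fm, does not depend on them.

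Finally, no inference or decision uses these parameters. The bioavailability model uses Cmax and the two AUCs, and cohort success and dose adjustment rest on lipid values. This limits the importance of the point. None of these replies answers the metabolite point, because nothing in either document confines clearance or volume to the parent drug.

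**Conclusion.** The metabolite point holds. As written, the plan calls for clearance and VDss of 2-hydroxy and 4-hydroxy atorvastatin, and values based on the parent dose would be CL_m/fm and an apparent volume. Clearance would be overstated 2 to 10 times for an assumed fm of 0.5 to 0.1, and not at all only if fm were 1. The conclusion assumes that the calculation uses the parent dose, the only dose the documents provide.

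For SC parent drug the finding is an inconsistency to reconcile: VDss in all three SC-related lists, and plain CL in the SAP multi-dose list and in protocol section 7, against Table 4.

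The effect is confined to descriptive PK endpoints. It would be wrong to read it as a threat to the relative bioavailability analysis or to the LDL-C-based decisions; neither changes. This is a minor point that is worth correcting because the parameters are named endpoints.

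**What to change.** - In SAP section 3 and protocol section 7, align the lists with Table 4: CL and VDss for IV parent drug only; CL/F and Vz/F for SC parent drug, including Cohort 4.
- In SAP 5.7.2, state that clearance and volume terms are not reported for the two metabolites, or are reported only as apparent values labelled CL_m/fm (and the corresponding apparent volume).
- For the metabolites keep Cmax, AUC, half-life and Kel. A metabolite-to-parent AUC ratio would describe the change in ratios noted in protocol section 5.4 directly; it is an optional addition, not part of the correction.

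The cost is wording in two documents and fewer rows in the PK tables. It needs no new samples or data.

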4.1 Study Measurements

4.1.1 Efficacy Measurements

The main efficacy measurements are the assessments of the LDL-C and HDL-C levels and the mean change in LDL-C in the injectable atorvastatin administration for each dosing cohort.

To assess the main efficacy objectives of the study, the lipid profile (including LDL-C and HDL-C) will be measured at the Screening Visit and Day 15, and the LDL-C level will be measured at Day 8.

4.1.2 Pharmacokinetic Measurements

The PK measurements in each dosing cohort are the assessments of plasma concentrations of atorvastatin and its metabolites (2-hydroxy atorvastatin and 4-hydroxy atorvastatin) in the oral administration and the administrations by the injectable route.

At the oral PK visit (Screening Period), serial PK blood samples to measure plasma concentrations of atorvastatin and its metabolites will be collected within 60 minutes prior to taking the oral dose of atorvastatin, at 30 minutes (\pm 5 minutes), 1, 2, 4, 6, and 8 h (\pm 10 minutes) after taking the oral dose.

Levels of atorvastatin and metabolites measured from the pre-dose (oral) timepoint are imputed as 24-hour levels since the subject is on daily, constant dosing.

In the last dose of injectable atorvastatin at Day 15 visit, serial PK blood samples to measure plasma concentrations of atorvastatin and its metabolites will be collected within 60 minutes prior to the start of the dose, immediately after completion of IV dose (within 3 to 7 minutes), at 30 minutes (\pm 5 minutes), 1, 2, 4, 6, and 8 h (\pm 10 minutes) after completing the injected dose.

Levels of atorvastatin and metabolites measured from the pre-dose (IV) timepoint are imputed as 24-hour levels since the subject is on daily, constant dosing.

In the sub-study for the single SC atorvastatin dose, serial PK blood samples to measure plasma concentrations of atorvastatin and its metabolites will be collected at 30 minutes (\pm 5 minutes), 1, 2, 4, 6, 8 (\pm 10 minutes) and 24 h (\pm 60 minutes) after the SC dose.

4.1.3 Safety Measurements

The safety and tolerability of study drug in each dosing cohort will be evaluated through:

- Incidence of treatment-emergent adverse events (TEAEs)
- Study discontinuation information
- Changes in clinical laboratory tests (CPK, ALT and AST)
- Vital signs (clinically significant changes in a subject will be recorded as AEs)

Adverse events (AEs) will be collected from the signing of informed consent form (ICF) to last subject contact/visit/end of post-treatment follow-up period.

Clinical laboratory tests including complete blood count (CBC), comprehensive metabolic panel (CMP), and lipid profile will be conducted at the Screening and, End Lead-in Visits, and at Day 15 or withdrawal.

Vital signs, including seated systolic blood pressure (SBP) and diastolic blood pressure (DBP), heart rate, respiration rate and body temperature, will be measured at the Screening Visit, between 30 and 0 minutes before the start of investigational medicinal product (IMP) and at 15 (+ 5) minutes after the start of IMP on Day 1.

4.2 Randomization

There is no randomization planned in the study.

4.3 Blinding

This is an unblinded study. All subjects will be openly assigned atorvastatin injection and their daily dose will be known by the Investigator and the subject.

4.4 Sample Size Justification

The clinical goal of replacing stable oral dosing of atorvastatin with temporary injectable dosing is to maintain constant LDL-C levels during and following the replacement therapy window. Therefore, the target mean change in LDL-C is zero. Utilizing the standard biological variabilities of LDL-C and an associated, estimated standard deviation of 0.15, a sample size of 13 would provide 80% power to show that the mean change in LDL-C after switching to injectable dosing is less than 10% of baseline levels if the true mean change for the group is zero. A mean change in LDL-C of up to 10% is not considered to be clinically significant over a short, two-week period.

4.5 Data Handling

All subject data used for analysis will be displayed in listings.

Summaries for continuous variables will include the descriptive statistics for number of subjects (n), mean (arithmetic and geometric), standard deviation (SD), minimum (min), median, and maximum (max). Summaries for categorical (discrete) variables will include the number and/or percentage of subjects in a particular category.

Conventions for presentation of numerical data:

Minimum and maximum values will be presented to the same number of decimal places as the electronic Case Report Form (eCRF) data. Means and medians will be presented to one more decimal place than the eCRF data. Standard deviations will be presented to two more decimal places than the eCRF data.

Plasma concentration and PK parameters in tables and listings will be displayed with 3 significant figures as follows:

- (1) Values ≥ 0.0001 and < 1 will be reported with 3 significant figures (e.g., 0.0123).
- (2) Values ≥ 1 and < 10 will be reported with 3 significant figures (e.g., 1.02).
- (3) Values ≥ 10 and < 100 will be reported with 3 significant figures (e.g., 10.2).
- (4) Values ≥ 100 and < 1000 will be reported with 3 significant figures (e.g., 102).
- (5) Values ≥ 1000 will be reported with 3 significant figures (e.g., 1020).
- (6) Values = 0 will be reported as 0.

Values for T_{max} will be reported to 2 significant figures.

In the evaluation of both oral and injectable, multiple-dose PK, levels of atorvastatin and its metabolites measured from the pre-dose timepoint are imputed as the Hour 24 levels since the subject will have been on at least a two-week period of daily, constant dosing, and the pre-dose value will essentially be the Hour 24 level from the previously administered dose. This will relieve subjects from making an extra clinic visit.

Baseline is defined as the last value measured prior to the first dose of study drug.

Change from Baseline is defined as [Post-baseline Value – Baseline Value].

5 Data Analysis

5.1 Analysis Populations

The following analysis populations will be used to summarize the results from this study.

- **Enrolled Population:** All subjects who were eligible, signed informed consent and were assigned IMP.
- **Safety Population:** All subjects who received at least a partial dose of IMP. No treated subjects will be excluded from the safety population.
- **Efficacy Population:** A completed group of subjects that 1) finished the two-week treatment period, 2) provided a Day 15 LDL-C level, and 3) took the final targeted dose for that cohort comprise the four efficacy populations.
- **Pharmacokinetic Population:** All subjects in the Efficacy Population who have no major protocol deviations and who have sufficient plasma atorvastatin concentration data for reliable estimates of the key PK variables for each of the four baseline cohorts.
- **Bioavailability Population:** All subjects in the PK Population who have complete PK profiles for either the IV or the SC multiple-dose treatment. This population will be used for the bioavailability analysis of PO/IV and PO/SC, respectively.

The frequency and percentage of subjects in each population will be summarized by cohort. Subjects who are excluded from the analysis populations will be listed by cohort, subject and treatment.

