‡ The CMP, including liver enzymes and CK results must be reviewed by an Investigator before the subject is deemed eligible for treatment. The LDL result from this panel will not weigh in on the eligibility determination. Only the point of care result from LI End Visit determines eligibility.

§ PK sampling (oral PK) is performed at the Lead-in End visit. Samples are taken per [Section 9.3.4.1](#). The pre-dose sample serves as the Hour 24 level.

¶ On Day 1, vitals are measured twice: 1) between 30 and 0 minutes before the start of IMP, and 2) 15 (\pm 5) minutes after the start of IMP

|| PK sampling (Multi-dose PK) is performed on subjects that complete a Day 15 visit. Samples are taken per [Section 9.3.4.2](#). The pre-dose sample serves as the Hour 24 level.

△ PK sampling (SC PK) is performed On Day 22 for those subjects participating in the sub-study. A subcutaneous injection of IMP is administered on a day that oral atorvastatin is withheld, then samples are taken per [Section 9.3.4.3](#).

** If a subject withdraws (WD) from the treatment period before Day 15, the following assessments should be completed: Physical exam, CBC, CMP, lipid profile, vital signs. Withdrawn subjects do not have PK blood draws and are not eligible for the SC sub-study.

Table 9-1B **Schedule of Events**
for subjects NOT taking oral atorvastatin at study entry

Study Phase	Screen-ing	Lead-in			Treatment							Follow-up call	Optional SUB-STUDY	
Study Day	Day -3 to 0 from LI Day 0	LI Day 0	LI Interim Visit (LI Day 28 +/- 2 days)	LI End Visit (Interim visit + 7 to 10 days AND 0 to -2 days before Day 1)	Day 1	Day 2	Day 3	Days 4-7	Day 8	Days 9-14	Day 15	Day 22	Day 22 +/- 2 days	Day 29 +/- 3 days (Phone call)
LDL-C, Point of care	X*		X	X [†]										
LDL-C, Local										X				
Demographic Data	X													
Medical History	X													
Pregnancy Test, if	X			X								X		
Drug, Alcohol, Viral	X													
Physical Exam	X													
CBC, CMP, lipid profile	X			X [‡]								X		
Basic Metabolic Panel						X			X					
Vital Signs	X				X [†]									
Review of Eligibility	X			X										
PK Blood Draws				X [§]								X [¶]		X ^Δ
Dispense oral		X												
Daily oral atorvastatin dosing			X										Resume on Day 16, if in sub-study	
Drug accountability			X	X										
Daily IV or SC IMP									X					
Single injection SC													X	
Con Med monitoring					X								X	

Adverse Event		X	X
---------------	--	---	---

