§ PK sampling (oral PK) is performed at the Lead-in End visit. Samples are taken per protocol [Section 9.3.4.1](#). The pre-dose sample serves as the Hour 24 level.

¶ On Day 1, vitals are measured twice: 1) between 30 and 0 minutes before the start of IMP, and 2) 15 (\pm 5) minutes after the start of IMP

|| PK sampling (multi-dose PK) is performed on subjects that complete a Day 15 visit. Samples are taken per protocol [Section 9.3.4.2](#). The pre-dose sample serves as the Hour 24 level.

△ PK sampling (SC PK) is performed On Day 22 for those subjects participating in the sub-study. A subcutaneous injection of IMP is administered on a day that oral atorvastatin is withheld, then samples are taken per protocol [Section 9.3.4.3](#).

** If a subject withdraws (WD) from the treatment period before Day 15, the following assessments should be completed: Physical exam, CBC, CMP, lipid profile, vital signs. Withdrawn subjects do not have PK blood draws and are not eligible for the SC sub-study.

Table 3B: Schedule of Study Procedures for Subject's without Prior Oral Atorvastatin Use at Study Entry

Study Phase	Screen -ing	Lead-in			Treatment							Follow-up call	Optional SUB-STUDY		
		LI Day -3 to 0 from LI Day 0	LI Day 0	LI Interim Visit (LI Day 28 +/- 2 days)	LI End Visit (Interim visit + 7 to 10 days AND 0 to -2 days before Day 1)	Day 1	Day 2	Day 3	Days 4-7	Day 8	Days 9-14	Day 15	Day 22 +/- 2 days	Day 29 +/- 3 days (Phone call)	
Study Day													Day 22		
LDL-C, Point of care	X*		X		X†										
LDL-C, Local										X					
Demographic Data	X														
Medical History	X														
Pregnancy Test, if	X				X							X			
Drug, Alcohol, Viral	X														
Physical Exam	X														
CBC, CMP, lipid profile	X				X‡							X			
Basic Metabolic Panel							X		X						
Vital Signs	X					X§									
Review of Eligibility	X				X										
PK Blood Draws					X\$							X¶		XΔ	
Dispense oral		X													
Daily oral atorvastatin dosing				X									Resume on Day 16, if in sub-study		
Drug accountability			X	X											
Daily IV or SC IMP									X						

Single injection SC												X	
Con Med monitoring								X					X
Adverse Event									X				X

* Point of care LDL-C is the first procedure done after the subject gives consent. If the value does not meet eligibility, the subject screen fails and receives no other assessments. Otherwise, the subject continues into the full screening phase.

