5.7.1 Plasma Concentrations

Plasma concentrations of atorvastatin and its metabolites will be listed at each time point by cohort, subject and treatment, and summarized by route and final treatment cohort at each time point using descriptive statistics (n, arithmetic mean, SD and coefficient of variation (CV), geometric mean, geometric CV%, min, median and max).

Plots of individual concentrations of atorvastatin and its metabolites versus time, and mean plasma concentrations of atorvastatin and its metabolites versus the planned sampling time, will be presented on linear and semi-logarithmic scales.

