5.7.3 Relative Bioavailability Analysis

To compare the PK profile of atorvastatin and metabolites administered by the IV or SC route to that of oral administration, the relative bioavailability analysis will be performed for each cohort using key PK parameters (C_{max} , AUC_{0-24} and AUC_{inf}) of atorvastatin and, if data allow, its metabolites. Dose-normalized key PK parameters of the oral and IV (or SC) routes of administration will be log-transformed and analyzed using an analysis of variance (ANOVA) model including terms for treatment route as a fixed effect and subject as a random effect. The least squares geometric means ratio of atorvastatin oral vs IV (or SC) will be calculated. A 90% CI on the ratio of untransformed PK parameters will be derived through reverse transformation of the 90% CI for the difference in the log scale to the 90% CI for the ratio in the original scale.

When appropriate, the same analysis may be performed to compare the PK profile of the atorvastatin SC vs oral (Cohort 4).

The least-squares geometric means, ratio of the geometric means and 90% CIs on the ratio will be displayed.

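### The PK Population in SAP 5.1 is nested in the Efficacy Population, so valid PK profiles get no parameters if the dose was later superseded or the Day 15 LDL-C is missing

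*SAP*

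**What the plan says.** SAP 5.1 admits a subject to the Efficacy Population who "1) finished the two-week treatment period, 2) provided a Day 15 LDL-C level, and 3) took the final targeted dose for that cohort". The PK Population is "All subjects in the Efficacy Population who have no major protocol deviations and who have sufficient plasma atorvastatin concentration data", and the Bioavailability Population is "All subjects in the PK Population who have complete PK profiles for either the IV or the SC multiple-dose treatment". The three sets are nested, so the last two inherit the LDL-C and final-dose conditions.

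The PK analyses use these sets as follows:

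- SAP 5.7.2: "Pharmacokinetic parameters will be derived for atorvastatin and its metabolites for subjects in the PK population".
- SAP 5.7.1: concentrations are listed by cohort, subject and treatment, with no population named, and are "summarized by route and final treatment cohort at each time point".
- SAP 5.7.3: "Dose-normalized key PK parameters of the oral and IV (or SC) routes of administration will be log-transformed", with route as a fixed effect, subject as a random effect and a 90% CI for the ratio.

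Sampling carries neither condition. The protocol's schedule footnotes (Tables 9-1A and 9-1B) state: "PK sampling (Multi-dose PK) is performed on subjects that complete a Day 15 visit". The SAP's schedule footnotes agree. Protocol 8.4.3.2 bars from treatment anyone who did not complete the lead-in PK draws.

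**The concern.** Two of the four objectives in protocol section 6 are pharmacokinetic: to describe the IV profile and to explore the SC profile. Whether a concentration profile is valid depends on dosing, sampling and assay. It does not depend on whether an LDL-C result came back from the same visit, or on whether the sponsor later changed the cohort's dose.

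Superseded doses are part of the design. Under protocol 9.3.6.2.2 a cohort whose dose is adjusted restarts at the new dose, aiming for thirteen subjects. Anyone who completed Day 15 before the change has paired oral and injectable profiles that the SAP does not turn into parameters. At stake are some precision in the oral-to-injectable ratio and direct within-cohort evidence on how exposure moves with injectable dose. SAP 5.6 and 5.7.4 summarise lipid results by each IV dose, yet no exposure parameters would exist for the non-final doses.

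**Working it through.** The documents state no PK sample size, PK power or count of excluded profiles, so there is no plan figure to reproduce. The check is first one of definitions, then an illustration of size.

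**Who is lost**

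| Subject | Oral profile | Day 15 profile | PK parameters under SAP 5.1 and 5.7.2 |
|---|---|---|---|
| Completed Day 15 on the final dose, LDL-C reported | Yes | Yes | Yes |
| Completed Day 15 on a dose later superseded | Yes | Yes | None (fails the dose condition) |
| Completed Day 15, LDL-C missing | Yes | Yes | None (fails the LDL-C condition) |
| Ongoing when the dose was changed | Yes | No (withdrawn; protocol 9.3.6.2.1 and 10.2) | None; only an oral profile exists |

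A Day 22 SC profile can also lose its parameters if the IV dose it was matched to is later superseded. Sub-study entry itself requires review of the Day 15 LDL-C (protocol 8.4.4.1), so a missing LDL-C should not cause this loss. The Bioavailability Population covers multiple-dose treatment only, so the Day 22 loss falls on SAP 5.7.2 and not on the ANOVA.

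**How many superseded doses are possible**

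Protocol 9.3.6.2.2 caps each adjustment at 25% of the preceding dose. With full upward steps from the Table 9-4 starting dose, the 10 mg cohort runs 2, 2.5, 3.125, 3.906, 4.883, 5 mg: five steps, hence up to five superseded doses. The other two IV cohorts have the same ratio of maximum to starting dose (10/4 = 20/8 = 5/2 = 2.5), so the count is the same. Smaller or downward steps could give more; no adjustment gives none.

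**Illustrative size**

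For a paired log-scale comparison of n subjects, the 90% CI half-width is t(0.95, n−1) × s_w × √(2/n), with s_w = √ln(1 + CV²). The relative change does not depend on the CV:

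- n = 13: 1.782 × √(2/13) = 0.699
- n = 16 (3 extra pairs): 1.753 × √(2/16) = 0.620; ratio to n = 13 is 0.887, an 11% reduction
- n = 18 (5 extra pairs): 1.740 × √(2/18) = 0.580; ratio is 0.829, a 17% reduction

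The within-subject CV is not in the documents. Over an assumed 30% to 50%, the CI factor exp(half-width) is:

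| Assumed CV | n = 13 | n = 16 |
|---|---|---|
| 30% | ×/÷ 1.23 | ×/÷ 1.20 |
| 40% | ×/÷ 1.31 | ×/÷ 1.27 |
| 50% | ×/÷ 1.39 | ×/÷ 1.34 |

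At a CV of 30%, n = 18 gives ×/÷ 1.19.

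**The case against.** The strongest reply is that the final-dose restriction is the protocol's own choice. Protocol section 7 calculates PK parameters for the final cohorts, and SAP section 3 does likewise. That stands: for the per-cohort endpoint, the dose condition in SAP 5.1 is consistent with the protocol. It does not cover the LDL-C condition. The protocol defines no PK population, and the Day 15 LDL-C requirement in protocol 12.2 is written for the efficacy analyses.

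The reply is also right that both branches may be small. Day 15 lipid blood is drawn at the same visit as the PK samples (protocol 9.4.4.6), so a profile without an LDL-C should be rare. Dose changes can be triggered by Day 8 values, and ongoing subjects are then withdrawn without Day 15 PK. SAP Table 1 shows a single dose for the SC cohort, so superseded doses do not arise there. Protocol 8.4.4.2 keeps subjects out of the sub-study once three in their cohort have a Day 15 LDL-C above the limit. SAP 5.7.3 sets no equivalence bound, so no decision turns on the CI width.

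Three stronger readings are tempting but are not supported:

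- *The data are discarded.* SAP 5.7.1 names no population for the concentration listing, and SAP 5.1 lists excluded subjects. What is lost is parameters, final-cohort summaries and the ANOVA.
- *The PK sample is selected on each subject's LDL-C result.* Doses are dropped by cohort, whatever the individual's value, and a successful cohort of thirteen can contain two subjects above 125%.
- *The all-dose analysis should be primary.* It assumes proportional exposure across injectable doses, which the documents do not establish. Protocol 9.4.7 also allows a person who has started treatment to be rescreened, so one person could contribute twice.

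**Conclusion.** The point holds in a limited form. As written, SAP 5.1 and 5.7.2 give no parameters to some subjects whose oral and injectable profiles are valid. The LDL-C condition on the PK Population has no justification in the documents. The final-dose condition is justified for the protocol section 7 endpoint, but not as a bar to deriving parameters at all.

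The size is unknown and may be nil, since it depends on how many subjects completed Day 15 before a dose change. The 11% to 17% narrowing assumes 3 to 5 extra independent pairs in a cohort, a common within-subject variance and dose-proportional exposure. It describes a supplementary analysis only. This is an inexpensive improvement to the SAP, not a flaw that invalidates the planned PK results.

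**What to change.** In SAP 5.1, define the PK Population as treated subjects with no major deviation affecting PK and with sufficient concentration data for at least one route, regardless of Day 15 LDL-C and of whether the dose was the final one. Then:

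1. Derive and list parameters by actual dose (SAP 5.7.2).
2. Keep the final-dose subset as the primary per-cohort PK summary and bioavailability analysis, as protocol section 7 requires.
3. Add, as a supplementary analysis, the SAP 5.7.3 dose-normalised model on all paired profiles within each lead-in cohort. Link repeat profiles from a rescreened person to one subject identifier.

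The cost is SAP wording and some added output, with no new samples or subjects. The downside is that the supplementary ratio rests on dose proportionality across nearby injectable doses. The report should state this and show the ratio beside the final-dose result.
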